1.4.2.12. PRO 140 CD03 HIV Extension Study

PRO 140_CD03 study (open-label, 350 subjects, multi-center) seeks to evaluate the long term efficacy, safety and tolerability of PRO 140 SC as long-acting single-agent maintenance therapy in virologically suppressed subjects with CCR5-tropic HIV-1 infection. The study population includes up to 300 treatment-experienced HIV-infected adult patients who successfully completed PRO 140_CD03 HIV study and continue to demonstrate HIV-1 viral suppression.

This clinical study is currently ongoing.

1.4.2.13. PRO 140 CD06 Study

PRO 140_CD06 study (double-blind, 80 subjects, single-center) seeks to evaluate the evaluate comparability of PRO 140 formulation Batch Lot # 3-FIN-3143 versus formulation Batch Lot# 3-FIN-2618 as a one-time subcutaneous (SC) injection in healthy subjects under non-fasting conditions.

1.4.2.14. PRO 140 CD07 Study

CD07_TNBC study (open-label, two-part [Phase Ib: Up to 18 subjects; Phase II: 30 Subjects], multi-center) seeks to evaluate the efficacy, safety, tolerability and maximum tolerate dose (MTD)

CONFIDENTIAL Page 31 of 108

of leronlimab (PRO 140) when combined with carboplatin in patients with CCR5+ metastatic triplenegative breast cancer (mTNBC).

The study population includes patients with CCR5-positive, locally advanced or metastatic triple-negative breast cancer (mTNBC) who are naïve to chemotherapy in metastatic setting but have been exposed to anthracyclines and taxane in neoadjuvant and adjuvant settings (first-line).

This clinical study is currently ongoing.

1.4.2.15. CD08 mCRC Study

CD08_mCRC study (open-label, 30 subjects, multi-center) seeks to evaluate the effect on overall response rate (ORR) of Leronlimab (PRO 140) when combined with Regorafenib in patients with CCR5+, Microsatellite Stable (MSS), Metastatic Colorectal Cancer (mCRC).

The study population includes patients with CCR5+, Microsatellite Stable (MSS), metastatic Colorectal Cancer (mCRC) who have been previously treated with fluoropyrimidine-, oxaliplatin- and irinotecan-based chemotherapy, an antiVEGF therapy, and, if RAS wild type, an anti-EGFR therapy.

1.4.2.16. CD07 Compassionate Use

CD07_Compassionate Use study (open-label, two-part, multi-center) seeks to evaluate the efficacy, safety, and tolerability of leronlimab (PRO 140) when combined Treatment of Physician's Choice in the treatment of patients with CCR5+ Metastatic Triple Negative Breast Cancer (mTNBC). The study population includes patients with CCR5-positive, locally advanced or metastatic triplenegative breast cancer (mTNBC).

This clinical study is currently ongoing.

1.4.2.17. CD09 Basket Study

CD09_Basket study (open-label, 30 subjects, multi-center) seeks to evaluate the anti-tumor activity of leronlimab (PRO 140) in patients with CCR5+, locally advanced or metastatic solid tumors who have disease progression on standard therapy, or receiving a standard anticancer treatment but no subsequent approved treatment would be available upon progression, or unable to receive standard therapy, or for whom standard therapy does not exist.

This clinical study is currently ongoing.

1.4.2.18. CD10 COVID-19

CD10_COVID-19 (two-arm, randomized, double blind, placebo controlled) study seeks to evaluate the safety and efficacy of leronlimab (PRO 140) in patients with mild-to-moderate symptoms of respiratory illness caused by coronavirus 2019 infection. Patients were randomized to receive 2

CONFIDENTIAL Page 32 of 108

weekly doses of 700 mg leronlimab (PRO 140), or placebo via subcutaneous injection at Day 0 and Day 7.

The study population was 60.7% female and 39.3% male, with an average age of 54.85 years. There were 56 subjects treated with leronlimab (PRO 140) and 28 with placebo.

CD10 study did not meet the pre-defined primary endpoint (change in symptom score at Day 14 analyzed as a continuous variable) or any of the pre-defined secondary efficacy endpoints (time to clinical resolution; change from baseline NEWS score at Days 3, 7, and 14 analyzed by ANCOVA method; change from baseline in pulse oxygen saturation Days 3, 7, 14; change from baseline health status by 7-point category ordinal scale at Days 3, 7, and 14; Incidence and Duration of hospitalization; incidence and duration of mechanical ventilation; incidence and duration of oxygen use; mortality at Day 14, or time to return to normal activity).

Post-hoc analyses described below, however did provide additional insights and information which helped design the further development of PRO 140 in COVID-19

[figure not shown]
- Day 3 total symptom score results:
 - 62.96% of the 56 subjects in PRO 140 group showed improvement in total symptom score, compared to 56% of the 28 subjects in the placebo group. In the sub-population of subjects with baseline total symptom score of \geq 4, 90% of subjects treated with leronlimab (PRO 140) were reported with improvement in total symptom score, compared to 71% of subjects in the placebo group.
- National Early Warning Score 2 (NEWS2) (reported as proportion):

24 of 56 (50%) of subjects treated with leronlimab (PRO 140) showed improvement from baseline in NEWS2 score at EOT visit, compared to 5 of 28 (20.83%) of subjects in the placebo group .

Safety was assessed primarily via reporting of adverse events (AEs) and serious adverse events (SAEs) throughout the study. In total, 34% (19 of 56 subjects) treated with leronlimab compared to 50% (14 of 28 patients) treated with placebo reported at least one AE. Additionally, 9% of subjects (5/56) reported SAEs in leronlimab group compared to 21% of subjects (6/28) in the placebo group.

The vast majority of the patients with mild to moderate COVID-19 recover with supportive care. The study sample size was not large enough to evaluate the effect of PRO 140 in this patient population. Post-hoc analyses indicate the potential for benefit of PRO 140 in patients with more severe (total symptom score of ≥4) COVID-19. Safety data shows that leronlimab (PRO 140) was well tolerated by subjects. The incidence, frequency, and severity of AEs and SAEs were not increased in the leronlimab (PRO 140) group compared to the placebo group.

CONFIDENTIAL Page 33 of 108

List of Completed Clinical Studies with Leronlimab (PRO 140) **Table 1-1:**

Protocol Number	Phase	No. of Subjects (Planned/ Analyzed)	Doses	Subject Population	Comments
PRO 140 1101	1	20/20	Single 0.1, 0.5, 2.0, or 5.0 mg/kg	Healthy	Generally well tolerated; non-immunogenic; dose-dependent coating of CCR5; significant coating of CCR5 over placebo at 0.5, 2, and 5 mg/kg
PRO 140 1102	1	20/20	Either two or three doses totaling 200 or 350 mg respectively	Healthy	Generally well tolerated; drug derived from CHO cells well tolerated also; SC administration by Autoject® 2 better tolerated than manual injection
PRO 140 1103	1	15/14	Two doses, each of 350 mg	Healthy	More AEs associated with arm injection; trend of lower exposure in arm injections; thigh and abdominal administration preferred
PRO 140 1302	1b	40/39	Single 0.5, 2.0, or 5.0 mg/kg	HIV-1 positive	Generally well tolerated; antiviral suppression maintained for approx. 10 days with higher doses; favorable tolerability and potent, dose- dependent antiviral activity provide proof-of- concept
PRO 140 2301	2a	30/31	Single 5.0 or 10.0 mg/kg	HIV-1 positive	Generally well tolerated with no dose-limiting toxicities; potent antiviral suppression maintained for approx. 20 days when administered IV at 5 or 10 mg/kg. No dose-limiting toxicities at 10 mg/kg.
PRO 140 2101	2a	40/44	Three doses of 162 or 324 mg each	HIV-1 positive	Generally well tolerated, no drug-related SAEs or dose-limiting toxicity; antiviral activity was statistically significant; two-fold exposure at higher dose; single dose demonstrated favorable tolerability, and potent, long-acting, dose-dependent antiviral activity.
PRO 140 CD01	2b	43/43	350 mg SC weekly dose for 12 weeks of monotherapy (total treatment duration 14 weeks)	HIV-1 positive	Generally well tolerated, no drug-related SAEs or dose-limiting toxicity; Open-label administration of PRO 140 demonstrated favorable tolerability, and potent, long-acting, antiviral activity.

CONFIDENTIAL Page 34 of 108

Date: 28-Dec-2020

Protocol Number	Phase	No. of Subjects (Planned/ Analyzed)	Doses	Subject Population	Comments
PRO 140 CD02	2b/3	50/52	350 mg SC weekly dose of PRO 140 or placebo along with existing ART for 1 week then PRO 140 along with optimized background therapy for 24 weeks (total treatment duration 25 weeks)	HIV-1 positive, treatment- experienced	This study is completed pending database lock.
PRO 140 CD06	PK	80/79	Single dose PK study with 350 mg SC dose	Healthy	This clinical study is completed.
CD10_CO VID-19	2	75/86	700 mg SC weekly dose or placebo	Mild to moderate COVID_19	This clinical study is completed and pending final clinical study report.

Table 1-2: List of Ongoing Clinical Studies with Leronlimab (PRO 140)

Protocol Number	Phase	No. of Subjects (Planned/ To be analyzed)	Doses	Subject Population	Comments
PRO 140 CD_01- Extension	2b	17/16	350 mg SC weekly dose (as monotherapy)	HIV-1 positive, treatment experienced	This clinical study is currently ongoing.
PRO 140 CD02 Extension	2b/3	50/40	350 mg SC weekly dose in combination with Optimized Background Therapy (OBT)	HIV-1 positive, treatment experienced	This clinical study is currently ongoing.

CONFIDENTIAL Page 35 of 108

[figure not shown]
No. of Subjects **Protocol** Subject Phase Doses Comments Number (Planned/ To **Population** be analyzed) HIV-1 350 or 525 or 700 mg SC weekly PRO 140 dose for 46 weeks of positive, This clinical study is 2 350/TBD CD03 monotherapy (total treatment treatmentcurrently ongoing. duration 48 weeks) experienced HIV-1 PRO 140 350 or 525 or 700 mg SC weekly positive, This clinical study is CD03 2 350/TBD dose (as monotherapy) treatment currently ongoing. Extension experienced Phase Ib: Up PRO 140 to 18 subjects 350 or 525 or 700 mg SC weekly Triple negative This clinical study is 1a/2b Phase II: 30 CD07 dose (as monotherapy) breast cancer currently ongoing. Subjects CCR5+, Microsatellite Stable (MSS), CD08 mC 700 mg SC weekly dose in This clinical study is 2 30/TBD Metastatic RC combination with Regorafenib pending start-up. Colorectal Cancer (mCRC). CD07 Co 350 mg SC weekly dose (as Triple negative This clinical study is Comp 30/TBD mpassiona monotherapy or combination with . Use breast cancer currently ongoing. te Use Treatment of Physican's Choice) CCR5+, Locally CD09 Bas 350 or 525 or 700 mg SC weekly This clinical study is 2 30/TBD Advanced or ket dose (as monotherapy) currently ongoing. Metastatic Solid Tumors

Leronlimab (PRO 140) is a humanized IgG4, κ monoclonal antibody (mAb) specific for the type 5 C-C chemokine receptor (CCR5). Leronlimab (PRO 140) inhibits migration of Tregs into areas of inflammation which can inhibit the innate immune response against pathogens and most importantly, the migration of macrophages [Glass 2001] and release of pro-inflammatory cytokines in lungs. CCR5 engagement of macrophages changes them into effector cells rather than mediators of inflammation. In addition, the role of CCR5 antagonists in helping the innate immune response which is critical for infections the body has not been introduced to before (e.g. COVID-19), is discussed in Halama et al (2016).

The ARDS has known to be one of the main reasons for mortalities in patients with COVID-19. CytoDyn believes that leronlimab, CCR5 antagonist, is a potential therapeutics in inhibiting proinflammatory cytokines (cytokine storm) responses as observed in ARDS and thus could be useful in treatment of COVID-2019.

1.5.2. Rationale for Dose Selection and Treatment Duration

Leronlimab (PRO 140) is currently under development for the indication of HIV, Graft versus host disease (GVHD), metastatic triple negative breast cancer (mTNBC), and metastatic colorectal cancer (mCRC).

The safety profile of leronlimab (PRO 140) has been extensively evaluated in clinical trials. PRO 140 has been administered intravenously or subcutaneously to more than 750 healthy and HIV-1 infected individuals thus far, in Phase I/II/III studies. The drug has been well tolerated following intravenous administration of single doses of 0.5 to 10 mg/kg or up to 700 mg weekly doses as subcutaneous (SC) injection. Overall, 324 subjects have been exposed to PRO 140 350 mg SC weekly dose with the longest duration of exposure lasting 4 years. Similarly, more than 250 and 150 subjects have been exposed to PRO 140 525 mg and 700 mg SC weekly dose, respectively.

Available safety data from 131 subjects that received 700 mg dose in the ongoing PRO 140_CD03 study shows that less than 10% of subjects reported AEs considered definitely related to study treatment. All of these AEs were injection site reactions and considered to be mild or moderate in severity.

By severity, three subjects (2.3%, 3/131) reported AEs that were considered severe and two subjects (1.5%, 2/131) reported events that were deemed to be life-threatening. No events were considered related to the study treatment.

CONFIDENTIAL Page 39 of 108

[figure not shown]
Serious adverse events (SAEs) were reported for six subjects (4.6%, 6/131). None of SAEs were considered related to the study treatment.

[figure not shown]
Additionally, there have been four patients with severe COVID-19 infection treated with 700 mg leronlimab (PRO 140) under individual patient, emergency use INDs. The current data from these patients are provided in the Investigational Brochure (IB).

Leronlimab (PRO 140) 700mg will be administered once weekly for two weeks only in this study as most patients with mild to moderate COVID-19 disease fully recovery within 2 weeks of developing initial symptoms.

While leronlimab showed weak activity relative to the positive control (2D7, an anti-CCR5 antibody) in Study 300-TD-018, the IC50 values were: $59.1~\mu g/mL$ for RANTES, $21.2~\mu g/mL$ for MIP-1 α and $39.6~\mu g/mL$ for MIP-1 β . The modeled Cmax* for the proposed 700 mg weekly dose is $267.2~\mu g/mL$ which is 4.5-12.6-fold higher than the IC50 values for these cytokines. In addition, at leronlimab concentrations greater than 75 $\mu g/ml$ for RANTES and greater than 100 $\mu g/ml$ for MIP-1 α and MIP-1 β , inhibition of 80% or more was seen for these cytokines (Appendix, Figure 2 of Study 300-TD-018). Therefore, leronlimab is anticipated to inhibit these cytokines following the 700 mg once weekly dose regimen.

Figure 1-1: Dose-response curve for inhibition of CC-chemokine-induced calcium mobilization by PRO 140

^{*}The human Cmax was modeled for a dose of 700 mg once weekly in a 70 kg human subject. An interspecies population pharmacokinetic model was fit to available monkey and adult human data (concentration-time). Simulations were carried out to identify leronlimab serum concentration-time profiles (approximate to adults receiving 700 mg SC once weekly).

Leronlimab's role in the binding and signaling of chemokines MIP-1 α (CCL3), MIP-1 β (CCL4), and RANTES (CCL5) will be further evaluated in the Phase 2b/3 study. In addition, Cytokine and Chemokine Panel will include assessment of sCD40L, EGF, Eotaxin (CCL11), FGF-2, Flt-3 ligand, Fractalkine, G-CSF, GM-CSF, GRO alpha (CXCL1), IFN-alpha2, IFN-gamma, IL-1 alpha, IL-1

CONFIDENTIAL Page 40 of 108

beta, IL-1RA, IL-2, IL-2R, IL-3, IL-4, IL-5, IL-6, IL-7, IL-8 (CXCL8), IL-9, IL-10, IL-12 (p40/p70) IL-13, IL-15, IL-17A, IL-17E/IL-25, IL-17F, IL-18, IL-22, IL-27, IP-10 (CXCL10), MCP-1 (CCL2), MCP-3, M-CSF, MDC (CCL22), MIG (CXCL9), MIP-1 alpha (CCL3), MIP-1 beta (CCL4), PDGF-AA, PDGF-AB/BB, RANTES (CCL5), TGF-alpha, TNF-alpha, TNF-beta, and VEGF-A.

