8.10.4. Efficacy Analyses

Primary Analysis

The ITT population will be the primary population for the analysis of the efficacy endpoints of the study.

Primary Endpoint

CONFIDENTIAL Page 82 of 108

The primary endpoint for this study is the proportion of subjects with Mortality at Day 28 between leronlimab and placebo. The difference in the Day 28 mortality between the leronlimab and placebo treatment groups will be compared using Logistic regression model.

Secondary Endpoints

To maintain the trial-wise Type I error rate at 0.05, a closed test procedure will be used for the secondary endpoints. The order of the secondary endpoints will prospectively specified in the SAP.

Analysis of the secondary and exploratory endpoints will be summarized according to the variable type:

- Continuous data summaries will include:
 - o If the Normality assumption is met, Analysis of Covariance (ANCOVA) would be used.
 - If the Normality assumption is not met, a non-parametric method or a rank ANCOVA analysis i.e., an ANCOVA analysis on rank-transformed data will be used.
- Categorical data summaries will be based on Logit model will be used.
- Time-dependent data: Cox proportional hazards model will be used to analyze time dependent data and to depict the time to event data.

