 Incidence of transaminitis, defined as an increase in alanine aminotransferase (ALT) and/or aspartate aminotransferase (AST) to > 5 times the upper limit of normal.

- Incidence of subjects requiring Renal Replacement Therapy (RRT) after randomization
- Incidence of new bacterial, invasive fungal, or opportunistic infection
- Change in size of lesion area by chest radiograph or CT
- Change from baseline in serum cytokine and chemokine levels at Days 3, 7, and 14
- Change from baseline in CCR5 receptor occupancy levels for Tregs and macrophages at Days 3, 7, and 14
- Change from baseline in CD3+, CD4+ and CD8+ T cell count at Days 3, 7, and 14

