## 9.1 Summarizing and Tabulating the Collected Data

All data collected will be summarized according to the variable type:

- Continuous data summaries will include number of observations, mean, standard deviation, median, and minimum and maximum values.
- Categorical data summaries will include frequency counts and percentages.

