# 9.2 Analysis of Efficacy Data

The primary analysis will be conducted on the mITT population. The PP population will be used as a supportive analysis if there is at least 5% difference between the numbers of subjects in the two populations. All statistical tests for efficacy will be two-sided tests, with  $\alpha$ =0.05

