9.2.3.16 Change in size of lesion area by chest radiograph or CT

Change in size of lesion area by chest radiograph or CT will be summarized descriptively and compared using Logit model, adjusting for stratification factors.

9.2.3.17 Change from baseline in serum cytokine and chemokine levels at Days 3, 7, and 14

Change from baseline in serum cytokine and chemokine levels at Days 3, 7, and 14 will be summarized descriptively and compared using ANCOVA adjusting for stratification factors.

If the Normality assumption is not met, a non-parametric method or a rank –ANCOVA analysis i.e., an ANCOVA analysis on rank-transformed data will be used.

9.2.3.18 Change from baseline in CCR5 receptor occupancy levels for Tregs and macrophages at Days 3, 7, and 14

Change from baseline in CCR5 receptor occupancy levels for Tregs and macrophages at Days 3, 7, and 14 will be summarized descriptively and compared using ANCOVA adjusting for stratification factors.

If the Normality assumption is not met, a non-parametric method or a rank –ANCOVA analysis i.e., an ANCOVA analysis on rank-transformed data will be used.

9.2.3.19 Change from baseline in CD3+, CD4+ and CD8+ T cell count at Days 3, 7, and 14 Change from baseline in CD3+, CD4+ and CD8+ T cell count at Days 3, 7, and 14 will be summarized descriptively and compared using ANCOVA adjusting for stratification factors. If the Normality assumption is not met, a non-parametric method or a rank –ANCOVA analysis i.e., an ANCOVA analysis on rank-transformed data will be used.

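### Cytokine and chemokine endpoint: raw change with a rank fallback, no log scale and no named baseline covariate, would lose power and yield no between-arm ratio if concentrations are lognormal

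*Protocol*

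**What the plan says.** The endpoint is listed as exploratory in SAP 3.3: "Change from baseline in serum cytokine and chemokine levels at Days 3, 7, and 14". SAP 9.2.3.17 sets the analysis: the change is to be "summarized descriptively and compared using ANCOVA adjusting for stratification factors". If normality is not met, a non-parametric method or rank-ANCOVA applies: "an ANCOVA analysis on rank-transformed data will be used". Protocol 8.10.4 has the same two-step rule for continuous data: "If the Normality assumption is met, Analysis of Covariance (ANCOVA) would be used". Protocol 8.9.2 leaves the choice of covariates to the SAP, and SAP 9.2.3.17 names only the stratification factors.

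For these analytes neither document mentions a log transform, a ratio or geometric mean, or a rule for values below the assay limit. Descriptive summaries are planned (SAP 9.1): "Continuous data summaries will include number of observations, mean, standard deviation, median, and minimum and maximum values". Tests are two-sided at 0.05 (SAP 9.2).

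Protocol 1.5.2 gives the analyte list, which includes "IL-1RA, IL-2, IL-2R, IL-3, IL-4, IL-5, IL-6, IL-7, IL-8 (CXCL8), IL-9, IL-10", and says that the drug's role with MIP-1α, MIP-1β and RANTES will be evaluated further in this study. It states no analysis method. Footnote 19 of the schedule of assessments drops cytokine sampling from the open-label phase, so the randomized phase is the only source of these data.

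**The concern.** Serum concentrations cannot be negative, are usually right-skewed, and tend to respond to treatment in proportion. A fall from 1000 to 500 and a fall from 10 to 5 are the same halving: both are ln(0.5) = −0.69 on the log scale. As raw changes they are −500 and −5. Ranking the raw change keeps that ordering, so subjects who started high still sit at the extremes, and the rank fallback does not remove the dependence on starting level.

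Two things are at stake. Real effects on the chemokines behind the rationale are more likely to be missed. And where ranks are used, the trial has no between-arm estimate with a confidence interval on a concentration or ratio scale.

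**Working it through.** **The plan's own figure.** The only powered endpoint is Day 28 mortality (SAP 4: 45% versus 30%, 2:1, two-sided 0.05, 80% power). The unpooled formula gives a placebo n of (1.96 + 0.8416)² × [0.45×0.55 + 0.30×0.70/2] / 0.15² = 7.849 × 0.3525 / 0.0225 = 122.97. That is 123 placebo and 246 leronlimab, as stated. The text available gives no power, SD or effect for cytokines.

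**Inputs for the check.**
- From the SAP: 246 and 123 completers, two-sided 0.05, three clinical-status strata.
- Assumed: lognormal baseline and follow-up values, log SD 0.8 or 1.2, baseline/follow-up correlation ρ of 0.3, 0.5 or 0.7, a true 25% reduction, and strata shifting the log level by 0.4 per step.

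**Formula for the log-scale methods.** The effect is |ln 0.75| = 0.2877, and √(1/123 + 1/246) = 0.1104. The residual SD is SD×√(1−ρ²) with log baseline as covariate, and SD×√(2(1−ρ)) for log change without baseline. At SD 1.2 and ρ 0.5:
- log follow-up on log baseline: 1.2 × 0.866 × 0.1104 = 0.1148; 0.2877/0.1148 = 2.51; power Φ(2.51 − 1.96) ≈ 71%
- log change, no baseline: 1.2 × 1.0 × 0.1104 = 0.1325; 0.2877/0.1325 = 2.17; power Φ(2.17 − 1.96) ≈ 58%

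**Simulated power (%).** All models include the strata. There were 3000 to 4000 runs per setting, so the simulation standard error is at most √(0.25/3000) = 0.9 points.

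| log SD, ρ | Raw change | Rank of change, no baseline | Rank of change, ranked baseline | Rank of follow-up, ranked baseline | Log change, no baseline | Log follow-up, log baseline |
|---|---|---|---|---|---|---|
| 0.8, 0.3 | 52 | 66 | 85 | 91 | 78 | 93 |
| 0.8, 0.5 | 63 | 78 | 90 | 95 | 90 | 96 |
| 0.8, 0.7 | 80 | 94 | 97 | 99 | 99 | >99 |
| 1.2, 0.3 | 22 | 35 | 48 | 59 | 45 | 62 |
| 1.2, 0.5 | 24 | 44 | 55 | 67 | 58 | 70 |
| 1.2, 0.7 | 32 | 64 | 73 | 82 | 80 | 86 |

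Loss against the last column, in row order:
- rank of change, no baseline: 27, 18, about 5, 27, 26, 22
- rank of change, ranked baseline: 8, 6, about 2, 14, 15, 13

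Repeat runs moved individual entries by up to about 3 points, hence the rounded ranges of about 5 to 28 and 2 to 15.

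**Second calculation.** Here the effect was set so that log-scale ANCOVA has 80% power, with ρ 0.5 and log SD 0.3 to 1.5. Losses were 17 to 29 points for rank of change without baseline, 4 to 16 with ranked baseline, and 2 to 3 for rank of the follow-up value with ranked baseline. Shapiro-Wilk rejected normality of the raw-change residuals in at least 98.8% of runs, so the fallback would nearly always be used. (The SAP names no normality test; this one is assumed.)

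**Type I error.** Under no effect, all methods rejected in 4.2 to 5.3% of runs.

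**Values below the assay limit.** With 40% of values below the limit, set to half of it (log SD 1.0, ρ 0.5), log-scale ANCOVA falls to 71.6% and rank of change with ranked baseline to 61.7%. The gap is still about 10 points.

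**The case against.** - *The inputs are assumed.* This stands. The text available gives no cytokine SD, correlation or effect. The protocol's list of tables includes Table 1-4 on cytokine levels after leronlimab, which is not in that text and may bear on the spread. The potency argument in Protocol 1.5.2 concerns chemokine signalling in vitro, so it does not supply the 25% fall in serum levels.
- *The SAP leaves the model open.* This also stands. A reader might infer that the plan carries one fixed power cost. It does not. The word ANCOVA may be meant to include baseline, and a rank analysis of the follow-up value with ranked baseline would lose only about 1 to 4 points in the table. That reading departs from the text, though, which names change from baseline as the variable and only the stratification factors as covariates.
- *Effect sizes will be reported.* A reader might infer that the trial will have no usable effect information. The planned arm-level means and medians contradict that. What is missing under ranks is a between-arm estimate with a confidence interval.
- *A log transform alone is enough.* The table does not support this. Log change without baseline is matched or beaten by rank-ANCOVA of the follow-up value with ranked baseline in all six settings. Much of the gain comes from adjusting for baseline.
- *The consequence is small.* Agreed. The endpoint is exploratory, unpowered, and outside the fixed sequence in SAP 8.4.

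**Conclusion.** The point holds as a low-cost improvement. As written, SAP 9.2.3.17 compares raw change with a rank fallback and names neither a log scale nor baseline. Given lognormal concentrations, a multiplicative effect and the ranges above, the fallback is what would be used. It would cost about 5 to 28 points of power without baseline, or about 2 to 15 with ranked baseline, against log-scale ANCOVA with log baseline, and it would leave no between-arm ratio with an interval.

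These sizes depend on the assumptions and on how the open model choice is settled. Nothing here suggests inflated false-positive rates or any effect on the primary or secondary analyses.

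**What to change.** In SAP 9.2.3.17:
- Analyse the log follow-up concentration at each of Days 3, 7 and 14 by ANCOVA with log baseline and the stratification factors.
- Report the between-arm geometric mean ratio with 95% CI.
- State a convention for values below the assay limit, for example half the limit.
- Keep the rank analysis as a sensitivity analysis, and as the main analysis for analytes mostly below the limit. State its response variable and whether ranked baseline is included.

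The cost is a few lines of SAP text and a transform in the program, with no new data. The downside is that the convention for values below the limit is arbitrary and matters more as the share of such values grows. If treatment codes are already open when the change is made, label the log-scale analysis as post hoc.
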